4.2 Exclusion criteria

- Patients who have undergone systemic chemotherapy, radiotherapy, surgery, hormone therapy, or immunotherapy <2 weeks before enrollment. Immune checkpoint blockade as pretreatment is permitted.
- 2. Patients with a history of taking regorafenib.
- Patients with hypertension that is difficult to control (systolic blood pressure ≥150 mmHg and diastolic blood pressure ≥90 mmHg) despite treatment with several hypotensive agents
- Patients with acute coronary syndrome (including myocardial infarction and unstable angina), and with a history of coronary angioplasty or stent placement performed within 6 months before enrollment
- 5. Patients with a large amount of pleural effusion or ascites requiring drainage.
- 6. Patients with a \geq grade 3 active infection according to NCI-CTCAE version 4.03
- 7. Patients with symptomatic brain metastasis
- 8. Patients with partial or complete gastrointestinal obstruction
- 9. Patients with interstitial lung disease with symptoms or signs of activity
- Patients who test positive for either anti-HIV-1 antibodies, anti-HIV-2 antibodies, anti-HTLV-1 antibodies, hepatitis B surface antigen (HBsAg), or anti-hepatitis C virus (HCV) antibodies*
 *Patients who test positive for either anti-HBs or anti-HBc antibodies, and those who have HBV-DNA measurements greater than the detection sensitivity will also be excluded. (However, patients with hepatocellular carcinoma in the expansion cohort will not be excluded even if they test positive for HBsAg and anti-HCV antibodies.)
- 11. Patients with concurrent autoimmune disease, or a history of chronic or recurrent autoimmune disease
- 12. Patients who require systemic corticosteroids (excluding temporary usage for tests, prophylactic

administration for allergic reactions, or to alleviate swelling associated with radiotherapy) or immunosuppressants, or who have received such a therapy <14 days before enrollment in the present study

- Patients with a history or findings of ≥grade III congestive heart failure according to the New York Heart Association functional classification
- 14. Patients with a seizure disorder who require pharmacotherapy
- 15. Major surgical procedure or significant traumatic injury within 28 days before start of study medication.
- 16. Patients undergoing major surgery (thoracotomy or laparotomy, etc.), laparotomy biopsy, trauma within 28 days before registration. The same day of the week before 4 weeks can be registered

(However, in case of an artificial anastomosis without intestinal resection, it shall be within 14 days before registration).

- 17. Non-healing wound, non-healing ulcer, or non-healing bone fracture
- 18. Patients with a history of hypersensitivity to any of the study drugs, similar drugs, or excipients.
- 19. Pregnant women, lactating women or possibly pregnant women.
5 Enrollment

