| | 8. For women who are likely to become pregnant (including those without |
| | menstruation due to medical reasons such as chemical menopause) Note 1, we |
| | agreed to double contraceptive Note 2 for at least 5 months after the final |
| l | administration of the investigational product from consent acquisition patient. |
| l | Also, patients who agreed not to breast feeding for at least 5 months after the final |
| | investigational drug administration after acquiring consent. |
| | |

For men, patients agreeing to double contraceptive for at least 7 months after the final investigational drug administration from the time of starting investigational drug administration.

Note 1): A woman who is likely to become pregnant is a woman who has experienced menarche and is not undergoing sterilization surgery (such as hysterectomy, bilateral salpingo ligation or bilateral oophorectomy), a woman without menopause Everything is included. The definition after menopause shall be amenorrhea continuously for 12 months or more even though there is no noteworthy reason. Women who are using oral contraceptives or mechanical contraceptive methods (such as intrauterine contraceptive devices or barrier methods) are considered to be pregnant.

Note 2): With regard to contraception, it is necessary to use two of the vasectomy or condom of a male patient or male male, the uterine tube ligation of a female patient or the other woman, a contraceptive pessary, an intrauterine contraceptive device or an oral contraceptive I need to agree to heavy contraception.

Exclusion criteria

- Patients who have undergone systemic chemotherapy, radiotherapy, surgery, hormone therapy, or immunotherapy <2 weeks before enrollment. Immune checkpoint blockade as pretreatment is permitted.
- 2. Patients with a history of taking regorafenib.
- Patients with hypertension that is difficult to control (systolic blood pressure ≥160 mmHg and diastolic blood pressure ≥90 mmHg) despite treatment with several hypotensive agents
- 4. Patients with acute coronary syndrome (including myocardial infarction and unstable angina), and with a history of coronary angioplasty or stent placement performed within 6 months before enrollment
- 5. Patients with a large amount of pleural effusion or ascites requiring drainage.
- 6. Patients with a \geq grade 3 active infection according to NCI-CTCAE version 4.03
- 7. Patients with symptomatic brain metastasis

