From cycle 2 onward, the treatment will commence after verifying that the dosing criteria listed in section 6.3 have been satisfied. The start day for nivolumab will be defined as day 1, including the washout period even in the event of conflict with the criteria defined in 6.3, and one cycle will last 28 days. If nivolumab is terminated and treatment is resumed as regorafenib monotherapy, the subsequent day of regorafenib resumption will be defined as day 1. In such an instance one cycle will also last 28 days.

Treatment will continue until the "criteria for treatment termination" are satisfied.

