6.3.1.2 Dose adjustment for hypertension

When hypertension develops during regorafenib treatment, dose adjustments will be made at the discretion of the principal investigator (or subinvestigator) with reference to "Table 4: Dose adjustments for hypertension." Hypertensive subjects require careful observation and it is strongly recommended to administer suitable hypotensive treatment during regorafenib treatment. The selection of hypotensive drug will be determined by the principal investigator (or subinvestigator) upon consideration of the treatment guidelines for each institution participating in the trial.

Furthermore, in subjects who receive a dose reduction, when hypertension is controlled for at least one cycle, the dose of the investigational drug can be increased to the starting dose at the discretion of the principal investigator (or subinvestigator).

| NCI-CTCAE grade | Dose adjustment |
|---|---|
| Grade 2 Systolic blood pressure of 140–159 mmHg and/or diastolic blood pressure of 90–99 mmHg, or when the former is normal but diastolic blood pressure is increased > 20 mmHg and accompanied by symptoms. | Continue the dosing. If poorly controlled, consider a dose reduction. When accompanied by symptoms, withdraw treatment until the subject recovers from the symptoms, and diastolic blood pressure is restored to <90 mmHg. When resuming treatment, continue at the same dose level. |
| Grade 3 Elevated systolic blood pressure of ≥160 mmHg and/or diastolic blood pressure of ≥100 mmHg, or pharmacotherapy of two or more types, and greater intensive therapy than before is needed. | Withdraw treatment until the diastolic blood pressure is decreased below 90 mmHg and if there are accompanying symptoms, until the subject recovers from the symptoms. When resuming treatment, consider decreasing the dose. When hypertension cannot be controlled with the addition of new hypotensive drugs or with more intensive therapy, decrease the dose by one level. When grade 3 hypertension recurs despite decreasing the dose and hypotensive treatment, |

Table 4: Dose adjustment for hypertension

| | decrease the dose further by one level. |
|---|---|
| Grade 4 | Terminate the administration of the |
| Life-threatening (e.g., malignant hypertension, | investigational drug. |
| temporary or constant neuropathy, and | |
| hypertensive crises). | |

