8.2 Observation and test schedule

The observation and testing schedule is presented in Table 9. When the principal investigator (or subinvestigator) deems it necessary to perform additional tests or observations, they will be performed in addition to the schedule presented in Table 9.

Table 8.2 Schedule

| Cycle | Screening | Investigational drug administration period | Terminat | 30 days | Follo |
|-------|-----------|--|----------|---------|-------|
|-------|-----------|--|----------|---------|-------|

| | period (-14 days to day 0) | | Су | cle 1 | | Cycl | le 2 ards | ion date ^{d)} | after last dose ^{e)} | w-up perio d |
|--|----------------------------------|-----------------|---------------|---------------|---------------|---------------|---------------|---------------------------|----------------------------------|--------------------|
| Day Permissible rang | je | 1 | 8 | 15 | 22 | 1 | 15 | Day 0 to +7 | Day -3 to +7 | |
| Visit | | 0 | 0 | 0 | 0 | 0 | 0 | 0 | 0 | 0 |
| Treatment | | | | | | | | | |   |
| Regorafenib treatment | | \rightarrow | \rightarrow | \rightarrow | | \rightarrow | \rightarrow | | | |
| Compliance | | 0 | | | | 0 | | | | |
| Nivolumab treatment | | 0 | | 0 | | 0 | 0 | | | |
| Background, etc. | 1 | | | 1 | | | 1 | | | 1 |
| Consent acquisition | 0 | | | | | | | | | |
| Verification of inclusion criteria and exclusion criteria | 0 | | | | | | | | | |
| Subject background | 0 | | | | | | | | | |
| Body meas | 0 | | | | | | | | | |
| urem Weight ents | 0 | ₀ c) | | | | 0 | | 0 | 0 | |
| vital signs/PS Weekly BP monitoring for the first 6 weeks | 0 | 0 | 0 | 0 | 0 | 0 | 0 | 0 | 0 | |
| Combination drugs/therapies with adverse events | 0 | 0 | \rightarrow | \rightarrow | \rightarrow | \rightarrow | \rightarrow | \rightarrow | → | |
| Laboratory tests | | 1 | | | | | | 1 | | |
| Blood tests (blood count, biochemistry ^{g)}) | 0 | ₀ c) | 0 | 0 | 0 | 0 | 0 | 0 | 0 | |
| Urine analysis | 0 | ₀ c) | 0 | 0 | 0 | 0 | 0 | 0 | 0 | |

| Thyroid function | 0 | ₀ c) | | | | 0 | | 0 | | |
|------------------------------|-----------------|---|-------|---|--|---|--|---|---|---|
| Coagulation test | 0 | ₀ c) | | | | 0 | | 0 | | |
| Pregnancy test ^{a)} | 0 | | | | | | | | | |
| Tumor markers | 0 | ₍₎ c) | | | | 0 | | 0 | | |
| 12-lead ECG | 0 | ₍₎ c) | | | | 0 | | 0 | | |
| Infection test | _O b) | | | | | | | | | |
| Tumor evaluation | • | | | • | | | | | | |

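### Exclusion 3 gives two systolic limits (150 and 160 mmHg) and, read literally, lets patients enter at a blood pressure the protocol grades as 3

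*Combined protocol and SAP*

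**What the plan says.** Exclusion criterion 3 appears twice in the current version. Section 4.2 has "systolic blood pressure ≥150 mmHg and diastolic blood pressure ≥90 mmHg) despite treatment with several hypotensive agents"; the Summary has "systolic blood pressure ≥160 mmHg and diastolic blood pressure ≥90 mmHg) despite treatment with several hypotensive agents". Neither copy says how many agents count as several. No other criterion in either visible list limits blood pressure at entry.

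Table 4 in section 6.3.1.2 defines grade 3 by pressure as "Elevated systolic blood pressure of ≥160 mmHg and/or diastolic blood pressure of ≥100 mmHg". At that grade regorafenib is held until diastolic pressure is below 90 mmHg and any symptoms have resolved, and a lower dose is considered on restarting. The table has no systolic condition for restarting. For grade 2 the entry begins "Continue the dosing. If poorly controlled, consider a dose reduction".

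Table 4 is an on-treatment rule: "When hypertension develops during regorafenib treatment, dose adjustments will be made at the discretion of the principal investigator". The check before a cycle is similarly limited in section 6.1.1: "From cycle 2 onward, the treatment will commence after verifying that the dosing criteria listed in section 6.3 have been satisfied". Table 8.2 schedules vital signs at screening and on cycle 1 day 1, in the row headed "vital signs/PS Weekly BP monitoring for the first 6 weeks". Section 6.1 lets treatment start up to 14 days after enrolment, counting the day of enrolment.

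**The concern.** Hypertension is a leading regorafenib toxicity. Section 2.6.2 reports it in 34.5% of treated patients, and at grade 3 or above in 15.6%. An entry criterion for blood pressure should therefore be unambiguous and should keep out patients whose pressure is already at a level where the protocol would hold the drug.

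Exclusion 3 falls short in three ways. Its two copies disagree on the systolic limit. Both join the limits with *and* where Table 4 uses *and/or*, so one very high component is not enough to exclude. Both also cover only patients on several agents, so an untreated patient or one on a single drug has no entry limit. At stake is patient safety at the first dose of a combination whose safety, according to section 2.7.2, had not been confirmed.

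**Working it through.** The plan states no figure to reproduce, so the check applies the rules as written. S is systolic and D diastolic pressure in mmHg.

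- Table 4, grade 3 by pressure: S ≥160 or D ≥100. (Table 4 also has a treatment-intensity route to grade 3, which is not used here.)
- Section 4.2 excludes, on several agents: S ≥150 and D ≥90.
- Summary excludes, on several agents: S ≥160 and D ≥90.

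| Reading | Table 4 grade by pressure | 4.2, several agents | Summary, several agents | Either copy, one agent or none |
|---|---|---|---|---|
| 185/85 | 3 | eligible | eligible | eligible |
| 145/105 | 3 | eligible | eligible | eligible |
| 155/105 | 3 | excluded | eligible | eligible |
| 175/105 | 3 | excluded | excluded | eligible |
| 155/95 | 2 | excluded | eligible | eligible |
| 125/92 | 2 | eligible | eligible | eligible |

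In general, the grade 3 readings left eligible on several agents are:

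- Section 4.2: {S ≥160, D <90} and {D ≥100, S <150}.
- Summary: {S ≥160, D <90} and {D ≥100, S <160}.
- Difference: D ≥100 with S 150 to 159.

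A grid of whole-number readings (S 100 to 220, D 50 to 130, S above D) confirms this. Section 4.2 leaves 3494 grade 3 pairs eligible and the Summary 3804. The difference is 3804 − 3494 = 310, which matches 10 systolic values × 31 diastolic values (100 to 130). These are counts of grid points and say nothing about how many patients are affected.

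For the first dose, the pressure is measured on cycle 1 day 1, but section 6.3.1.2 covers hypertension arising on treatment and section 6.1.1 requires the section 6.3 check only from cycle 2. No visible text says which day 1 reading stops the dose. Because the first dose may come up to 14 days after enrolment, a limit at screening does not settle the day 1 reading either.

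Candidate corrections, applied to the same six readings:

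- S ≥150 or D ≥90, and S ≥160 or D ≥90: both exclude all four grade 3 readings, but also 155/95 and 125/92. If the several-agents condition stays, 175/105 on one agent is still eligible.
- S ≥160 or D ≥100, any number of agents: excludes exactly the four grade 3 readings.
- S ≥150 or D ≥100, any number of agents: excludes the four and 155/95, and keeps 125/92 eligible.

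**The case against.** The strongest reply is that the literal reading is not the intended one. The English is a rough translation, and *and* is used loosely elsewhere in the same list: exclusion 4 joins acute coronary syndrome to a history of stenting with it, and the hepatocellular carcinoma exception in exclusion 10 joins two viral markers. The criterion is also aimed at refractory hypertension, which calls for clinical judgement, and leaving out untreated patients can be a deliberate choice because they can be treated. Section 5.2 makes enrolment depend on an eligibility checklist that is not among the documents, so the limit sites actually apply cannot be known. The opening of chapter 6 also makes following its rules conditional on the subject not being at risk.

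Most of this is fair, and a translation slip is quite possible. But it cannot explain 150 against 160 mmHg, and judgement does not supply a limit that two current lists state differently.

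The safeguards after dosing starts are real: weekly pressure checks for six weeks, admission at the first dose with discharge allowed after the cycle 1 day 4 observations (section 2.8), strongly recommended antihypertensive treatment, and dose steps such as "When hypertension cannot be controlled with the addition of new hypotensive drugs or with more intensive therapy, decrease the dose by one level". They limit harm after exposure and do not set an entry limit.

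A reader might infer that every grade 3 reading admitted contradicts Table 4. The documents do not support that. The grade 3 hold ends once diastolic pressure is below 90 and symptoms have resolved, so an asymptomatic patient at 185/85 already meets the restart condition. The conflict is clearest for the group with diastolic ≥100.

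**Conclusion.** The point holds as an inconsistent and too loose entry criterion. The 150 versus 160 mmHg discrepancy is certain. That grade 3 readings are eligible follows exactly from the wording, on the assumption that *and* and the several-agents condition are meant literally. Most of the gap comes from those two features; the discrepancy adds only diastolic ≥100 with systolic 150 to 159, and only where a site follows the Summary.

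The documents do not allow the number of affected patients to be estimated, and it is probably small.

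A reader might also infer that dose escalation or the adverse event tables are distorted, because section 10.1.1 counts symptoms present at baseline only if their grade worsens. The documents do not show that any patient entered at grade 3 or how such a case would be judged for DLT, so no such effect is claimed. Nor do they show that anyone was enrolled unsafely. The change should be made because it is cheap and protects patients at the first dose.

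**What to change.** State one identical criterion in section 4.2 and the Summary:

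1. Exclude patients with systolic ≥160 mmHg or diastolic ≥100 mmHg at screening, whatever the number of antihypertensive agents. Use systolic ≥150 mmHg instead if the sponsor confirms that section 4.2 holds the intended limit.
2. Allow a patient over the limit to be treated and enrolled once controlled.
3. Apply the same limit to the vital signs already scheduled for cycle 1 day 1, before the first regorafenib dose.

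The choice of systolic limit has one consequence to settle knowingly. With 160/100, a patient on several agents at 155/95, whom section 4.2 now excludes, becomes eligible; with 150/100 that patient stays excluded.

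Do not simply replace *and* with *or* while keeping 90 mmHg, unless excluding grade 2 readings such as 125/92 is intended. That change would also leave patients on one agent or none uncovered.

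The cost is a wording change in two lists plus one day 1 dosing rule, with no new measurement. A few patients will need their blood pressure controlled before enrolment or before the first dose.

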- 8. Patients with partial or complete gastrointestinal obstruction
- 9. Patients with interstitial lung disease with symptoms or signs of activity
- 10. Patients who test positive for either anti-HIV-1 antibodies, anti-HIV-2 antibodies, hepatitis B surface antigen (HBsAg), or anti-hepatitis C virus (HCV) antibodies*
 *Patients who test positive for either anti-HBs or anti-HBc antibodies, and those who have HBV-DNA measurements greater than the detection sensitivity will

| | also be excluded. |
|----------------|---|
| | (However, patients with hepatocellular carcinoma in the expansion cohort will not |
| | be excluded even if they test positive for HBsAg and anti-HCV antibodies.) |
| | 11. Patients with concurrent autoimmune disease, or a history of chronic or recurrent |
| | autoimmune disease |
| | 12. Patients who require systemic corticosteroids (excluding temporary usage for |
| | tests, prophylactic administration for allergic reactions, or to alleviate swelling |
| | associated with radiotherapy) or immunosuppressants, or who have received such |
| | a therapy <14 days before enrollment in the present study |
| | 13. Patients with a history or findings of ≥grade III congestive heart failure according |
| | to the New York Heart Association functional classification |
| | 14. Patients with a seizure disorder who require pharmacotherapy |
| | 15. Patients who had grade 3 or higher bleeding during 4 weeks before enrollment. |
| | 16. Patients undergoing major surgery (thoracotomy or laparotomy, etc.), laparotomy |
| | biopsy, trauma within 28 days before registration. The same day of the week |
| | before 4 weeks can be registered |
| | (However, in case of an artificial anastomosis without intestinal resection, it shall |
| | be within 14 days before registration). |
| | 17. Non-healing wound, non-healing ulcer, or non-healing bone fracture. |
| | 18. Patients with a history of hypersensitivity to any of the study drugs, similar drugs, |
| | or excipients. |
| | 19. Pregnant women, lactating women or possibly pregnant women |
| Trial | The investigational drug will be repeatedly administered until the criteria for |
| participation | discontinuation are met. |
| period | In the event that the treatment is discontinued for reasons other than an exacerbation of |
| _ | the underlying disease via imaging (e.g., unacceptable side effects), tumor evaluation |
| | follow-up will continue until either an exacerbation of the underlying disease is |

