2.6.2 Summary of adverse events associated with regorafenib

Approximately 4000 safety analysis reports that received Regorafenib are listed in the study drug summary. Therapeutic-related adverse events with an incidence of over 20% were hand-foot syndrome (45.7%), fatigue (40.9%), loss of appetite (35.7%), diarrhea (34.7%), high blood pressure (34.5%%), Weight loss (27.9%), fever (21.4%). Adverse events of grade 3 and above with an incidence of over 5% were high blood pressure (15.6%), hand and foot syndrome (14.9%), fatigue (10.3%), diarrhea (5.9%), asthenia, (5.8% (5.7%). Severe adverse events that occurred during treatment with an incidence of > 1% were severe adverse events (8.1%), fever (2.4%), abdominal pain (2.2%), dyspnea (1.4%), pneumonia (1.3%), Diarrhea (1.2%), intestinal obstruction (1.1%).

Although many of the deaths occurring within 30 days of Regorafenib administration and within 30 days from discontinuation of treatment were disease progression, 65 cases of "adverse events not related to disease progression" or "toxicity related to investigational drugs" have been reported. Of 17 of them, it is judged that the association with regorafenib cannot be denied. Among them, rectal and vaginal bleeding (1 case), pulmonary bleeding (1 case), pulmonary embolism (1 case), pulmonary sepsis (1 case), femoral hematoma (1 case), cardiac arrest (4 cases) , A cardiopulmonary arrest (1 case), a heart failure (1 case), a cerebral vascular attack (1 case), a cerebral hemorrhage (1 case), a decrease in general health condition (1 case), sepsis (1 case), sudden death (1 case) It was acute liver failure (1 case).

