6.1 Protocol treatment

In the present trial, the protocol treatment will consist of the investigational drug, nivolumab, used in combination with regorafenib. However, in the event that the termination criteria are satisfied for one of these drugs, the trial investigator can consider continuing the treatment protocol with either nivolumab or regorafenib monotherapy upon deliberation with the trial coordinating committee. The treatment protocol will commence within 14 days of enrollment, including the day of enrollment. Furthermore, in the event that administration of the investigational drug cannot be initiated within 14 days of enrollment (including the day of enrollment), the trial coordinating committee is to be contacted to examine how the patient should be handled.

The following terminology is used in the present protocol:

- Termination: Administration of the investigational drug is not resumed.
- Washout: Omission of one or more doses of the investigational drug and moving onto the next dosing schedule.

• Washout period: The duration of time that the investigational drug is not administered.

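### The synopsis and Section 4 decide the same patient differently on five eligibility criteria, including whether a recent grade 3 bleed excludes the patient

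*Combined protocol and SAP*

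**What the plan says.** The protocol gives two complete eligibility lists: one in the Section 1 summary (the synopsis), the other in Sections 4.1 and 4.2. Both number the exclusions 1 to 19.

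- **Exclusion 15.** Synopsis: "Patients who had grade 3 or higher bleeding during 4 weeks before enrollment". Section 4.2: "Major surgical procedure or significant traumatic injury within 28 days before start of study medication".
- **Exclusion 16 (both lists).** Major surgery, open biopsy and trauma in the 28 days before registration, with the note "The same day of the week before 4 weeks can be registered". The limit is 14 days for an anastomosis without bowel resection.
- **Exclusion 3.** The synopsis defines uncontrolled hypertension as "systolic blood pressure ≥160 mmHg and diastolic blood pressure ≥90 mmHg" despite several agents. Section 4.2 has the same rule with a systolic limit of 150 mmHg.
- **Inclusion 7.** AST/ALT in hepatocellular carcinoma (HCC) may reach 100 U/L in the synopsis and 200 U/L in Section 4.1. Creatinine may reach 1.5 mg/dL in the synopsis and 1.5 times the upper limit of normal (ULN) in Section 4.1.
- **Exclusion 10.** A positive anti-HTLV-1 test excludes in Section 4.2 only. The infection tests in Table 8.1 and Section 8.4.4 do not include it.

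Older infection results are accepted for 6 months in Table 8.2 note b and for 12 months in Section 8.4.4. The Subjects row, the objectives and Section 2.8.1 describe a population that standard chemotherapy has failed or that cannot tolerate it. Inclusion 3 in both lists asks only for confirmed advanced or metastatic disease. No available text says which list governs. The text of Section 5.1 and the eligibility checklist are not in the public documents.

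**The concern.** Section 5.2 makes enrollment depend on a completed eligibility checklist, so someone has to turn one of these lists into that form. Section 4 is the formal criteria section. Followed as written, it does not stop a patient with a grade 3 bleed two weeks earlier. Section 2.6 describes regorafenib as antiangiogenic, and Section 2.6.2 includes fatal bleeding among the deaths for which a link to the drug could not be denied. One or two further sites are planned for the expansion cohort, and Section 13.4.1 requires every site to use a common protocol. Two readings of one protocol defeat that requirement. What is at stake is who receives the combination, and whether a later reader can say who was eligible.

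**Working it through.** **Step 1. Same patient, both lists.** The limits come from Section 1 and from Sections 4.1 and 4.2. The test patients are illustrative. The documents give no ULN for creatinine, so 0.8 to 1.2 mg/dL is assumed.

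| Criterion | Synopsis | Section 4 | Test patient | Synopsis | Section 4 |
|---|---|---|---|---|---|
| Grade ≥3 bleeding, 4 weeks | excluded | no rule | grade 3 bleed 2 weeks ago | out | in |
| Systolic, with diastolic ≥90 on several agents | ≥160 excluded | ≥150 excluded | 155/95 mmHg | in | out |
| AST/ALT in HCC | ≤100 U/L | 200 U/L | AST 150 U/L | out | in |
| Anti-HTLV-1 | no rule | excluded | positive | in | out |
| Creatinine | ≤1.5 mg/dL | ≤1.5 × ULN | 1.3 mg/dL, ULN 0.8 | in | out |
| Creatinine | ≤1.5 mg/dL | ≤1.5 × ULN | 1.7 mg/dL, ULN 1.2 | out | in |

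Creatinine: 1.5 × 0.8 = 1.20, 1.5 × 1.0 = 1.50 and 1.5 × 1.2 = 1.80 mg/dL. The two rules coincide only at a ULN of exactly 1.0 mg/dL. For AST/ALT, the synopsis HCC limit equals its own general limit of 100 U/L, so its exception does nothing and is probably the slip. The blood pressure disagreement is confined to systolic 150–159 mmHg with diastolic 90 or more.

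**Step 2. What the surgery half of item 15 adds.** Section 6.1 says "The treatment protocol will commence within 14 days of enrollment, including the day of enrollment", so the first dose falls k days after registration, with k from 0 to 13.

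- Item 16 looks back 28 days from registration, which is 28 + k = 28 to 41 days before the first dose.
- Item 15 looks back 28 days from the first dose, which is 28 − k = 28 down to 15 days before registration.

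For surgery or trauma before registration, item 15 therefore falls within item 16's window. The exception is the anastomosis allowance. Such an operation 20 days before registration passes item 16 (20 > 14). If it counts as major surgery and dosing starts that day, it fails item 15 (20 < 28). After registration, only item 15 covers the 0 to 13 days up to the first dose.

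**Step 3. Can an enrollment checklist apply that last part?** Under Section 5.2, enrollment is complete once the registration number is issued. A form completed before then cannot record a later injury, whichever list it follows. Item 15 works in that interval only as a pre-dose check.

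**Step 4. Reach into the analysis.** Section 12.3 removes clearly ineligible patients from the full analysis set (FAS). Section 12.12.2 reports efficacy on all enrolled patients and safety on the safety population, and uses the FAS only for an appendix list of excluded patients. Section 12.2 drops mistaken enrollments from all enrolled patients. Because the FAS then removes ineligible patients from that group, mistaken enrollment must mean something else.

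**Not counted.** Haemoglobin (visible only in the synopsis), the bilirubin unit (garbled in the synopsis) and the platelet-transfusion note (Section 4.1 only) may be editing or PDF residue.

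**The case against.** **The count.** The laboratory block shows editing marks in both places, and setting bilirubin aside while counting creatinine and AST/ALT could look uneven. But the creatinine line is clean in both lists, and the two HCC figures are legible. Dropping the whole block would still leave item 15, systolic pressure and HTLV-1, and the main consequence would be unchanged.

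**The effect on enrollment is unseen.** This stands. The checklist may already combine both lists, and the protocol sends eligibility queries to the principal investigator. Section 13.4.4 also allows a memorandum to settle interpretation. However, it defines a memorandum as an explanation that leaves the protocol's content unchanged, whereas choosing between 150 and 160 mmHg changes one of the two texts.

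**Timing.** Version 1.7 is dated 9 April 2020, and planned enrollment ended in October 2018. From 31 October 2018 that is 526 days, about 17 months. If enrollment had closed, new wording would change no one's entry. The documents do not say whether it had.

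**The population condition.** It is stated several times outside the lists, and both lists omit it equally. It is therefore a separate gap and not a conflict between them. It still matters, because the numbered items are what a checklist would normally copy.

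**Conclusion.** The text is wrong as written. Five criteria give opposite decisions for some patients, one test window conflicts (6 v 12 months), and one population condition is missing from both lists. Four of the five conflicts need no assumption; creatinine depends on the local ULN. The missing bleeding exclusion matters most. The textual finding is firm, since item 15 is filled in both lists with different content and a lost line cannot explain it. The effect on actual enrollment is unknown.

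The documents do not support four stronger inferences that a reader might draw:

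- *That ineligible patients entered, or that sites diverged.* The checklist and Section 5.1 are not visible.
- *That the trial's results change.* The reported populations are not defined by the lists, and FAS membership affects only an appendix listing.
- *That the fatal bleeds measure the harm.* Of the 17 deaths itemised in Section 2.6.2, 4 are bleeding or haematoma (rectal/vaginal, pulmonary, femoral, cerebral). That is 4/17 = 24%, or 4/4000 = 0.1% of those treated. The section does not say whether these patients had bled recently, so the figures show that the hazard exists and not the cost of the omission.
- *That a Section 4.2 checklist would catch surgery or trauma after registration.* Step 3 shows that it would not.

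**What to change.** 1. Add the grade 3 or higher bleeding exclusion to Section 4.2.
2. Put the condition on failure or intolerance of standard chemotherapy into inclusion 3 of both lists.
3. Set one value in both places for systolic pressure, HCC AST/ALT and creatinine. The sponsor chooses; for HCC, 200 U/L looks intended.
4. Add HTLV-1 to Table 8.1 and Section 8.4.4, or delete the exclusion. State one look-back window for infection tests.
5. Merge exclusions 15 and 16 in both lists, say whether the 14-day anastomosis allowance survives, and apply the surgery/trauma rule again before the first dose.
6. Check haemoglobin, bilirubin and the transfusion note against the source file.
7. State that Section 4 as corrected governs, and match the checklist to it.
8. If enrollment has closed, record which list was applied and list every enrolled patient who meets only one of them.

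The cost is wording and a matching checklist, plus one screening blood test per patient if the HTLV-1 exclusion stays. No extra patients are needed. Step 8 is a one-time check of 39–48 planned patients (9–18 plus about 30, by the synopsis and Section 2.8.2) or 42–48 (12–18 plus about 30, by Section 12.8). Any patients added under the Section 2.8.2 option, around 10 per cancer type, come on top.
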